9.4.3.2. Comorbidities

The following comorbidities will be identified based on the presence of at least one ICD-9-CM/ICD-10-CM diagnosis code or NDC/HCPCS codes identified using all available data during the baseline period and are operationalized in Table 4.

Table 4. Operationalization of comorbidities			
History or presence of upper gastrointestinal anatomic or motor disorders	Operationalization: ICD-10-CM code	Operationalization: ICD- 9-CM code	
Esophageal strictures, webs, diverticula, or other gastroduodenal pathology seen on esophagogastroduodenoscop y	K22.2 Esophageal obstruction K57 Diverticular disease of intestine K22.5 Diverticulum of esophagus, acquired K31.5 Obstruction of duodenum Q39.3 Congenital stenosis and stricture of esophagus Q39.4 Esophageal web	530.3 Stricture and stenosis of esophagus 537.3 Other obstruction of duodenum 530.6 Diverticulum of esophagus, acquired 562 Diverticula of intestine 750.3 Congenital tracheoesophageal fistula, esophageal atresia and stenosis	
Gastrointestinal strictures of any kind	K56.69x Other intestinal obstruction K50 Crohn's Disease	555 Regional enteritis 560.9 Unspecified intestinal obstruction, Enterostenosis; of intestine or colon: obstruction, occlusion, stenosis, stricture.	
Esophageal or gastric motor disorders (eg, scleroderma)	C15 Malignant neoplasm of esophagus Z85.01 Personal history of malignant neoplasm of esophagus K31.84 Gastroparesis K91.1 Postgastric surgery	150 Malignant neoplasm of esophagus 530 Diseases of esophagus 787.1 Heartburn V10.03 Personal history of malignant neoplasm of esophagus	

		T
	syndromes K20 Esophagitis K21 Gastro-esophageal reflux disease K22 Other diseases of esophagus R12 Heartburn K30 Functional dyspepsia K23 Disorders of esophagus in diseases classified elsewhere Q39 Congenital malformations of esophagus	536.3 Gastroparesis 564.2 Postgastric surgery syndromes 750.3 Congenital tracheoesophageal fistula, esophageal atresia and stenosis 750.4 Other specified congenital anomalies of esophagus 536.8 Dyspepsia and other specified disorders of function of stomach
Barrett's esophagus	K22.7x Barrett's esophagus	530.85 Barrett's esophagus
Peptic ulcer disease, erosive gastritis and/or erosive duodenitis	K25 Gastric ulcer K26 Duodenal ulcer K27.x Peptic ulcer, site unspecified K28 Gastrojejunal ulcer	531 Gastric ulcer 532 Duodenal ulcer 533 Peptic ulcer site unspecified 534 Gastrojejunal ulcer
Eosinophilic esophagitis by histology (eosinophils per high powered field)	K20.0 Eosinophilic esophagitis	530.13 Eosinophilic esophagitis
Gastrointestinal malabsorption	K90 Intestinal malabsorption	579 Intestinal malabsorption
H. pylori infection within the past 6 months	B96.81 Helicobacter pylori [H. pylori] as the cause of diseases classified elsewhere	041.86 Helicobacter pylori [H. pylori]

Cystic Fibrosis	E84 Cystic fibrosis	277.0x Cystic fibrosis
	E84.8 Cystic fibrosis with other manifestations	
Diagnosed as having or has received treatment for esophageal, gastric, pyloric channel, or duodenal ulceration		
Proton pump inhibitors	Operationalization: NDC code	Operationalization: HCPCS code
Omeprazole (Prilosec)	70515062501	-
Esomeprazole (Nexium)	00186504054, 00186504005, 00186504031	-
Lansoprazole (Prevacid)	64764054130, 64764054105, 64764054111, 64764054119	-
Rabeprazole (AcipHex)	62856024330	-
Pantoprazole (Protonix) HCPCS Source	00008092351, 00008092355, 00008092360	S0164 Injection, pantoprazole sodium, 40 mg
H2-blockers		
Famotidine (Pepcid AC, Pepcid Oral) HCPCS Source	16837087210, 16837087220, 16837087222, 16837087230, 16837087231,	J3490 Unclassified drugs

Version 2.0, 10 February 2022			
	16837087260, 16837087275, 16837087290		
Cimetidine (Tagamet, Tagamet HB)	63029022201, 63029022202, 63029022203, 63029022204, 63029022205, 63029022270	-	
Ranitidine (Zantac, Zantac 75, Zantac Efferdose, Zantac injection, and Zantac Syrup) HCPCS Source	52565-102, 67751015101(for 150, max strength), 00173036238	J2780 Injection, ranitidine hydrochloride, 25 mg	
Nizatidine Capsules (Axid AR, Axid Capsules, Nizatidine Capsules)	65726-144-15, 65726-145- 10	-	

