9.4.2. Outcomes of interest

The outcomes of interest are listed in Table 3 below. These outcomes were based on the Investigator's Brochure (version 4.0 June 2021) and expert clinical judgment. The first occurrence of each outcome is defined based on the presence of at least one ICD-9-CM or ICD-10-CM diagnosis code identified in the inpatient or outpatient setting during the follow-up period.

Outcome of interest	Operationalization: ICD-10-CM code	Operationalization: ICD-9-CM code
Agranulocytosis	D70.2 Other drug-induced agranulocytosis D70.1 Agranulocytosis secondary to cancer chemotherapy	288.03 Drug induced neutropenia
Thrombocytopenia	D69.3 Immune thrombocytopenic purpura D69.59 Other secondary thrombocytopenia D69.6 Thrombocytopenia, unspecified D69.41 Evans syndrome D69.49 Other primary thrombocytopenia	287.31 Immune thrombocytopenic purpura 287.49 Other secondary thrombocytopenia 287.5 Thrombocytopenia, unspecified 287.30 Primary thrombocytopenia, unspecified 287.32 Evans syndrome 287.39 Other primary thrombocytopenia
Leukopenia	D72.810 Lymphocytopenia D72.818 Other decreased white blood cell count D72.819 Decreased white blood cell count, unspecified D70.8 Other neutropenia D70.9 Neutropenia, unspecified D70.0 Congenital agranulocytosis	288.51 Lymphocytopenia 288.59 Other decreased white blood cell count 288.50 Leukocytopenia, unspecified 288.09 Other neutropenia 288.00 Neutropenia, unspecified
Pancytopenia	D61.811 Other drug-induced pancytopenia	284.12 Other drug-induced pancytopenia
	D61.818 Other pancytopenia	284.19 Other pancytopenia

Hypersensitivity (including anaphylactic reactions and anaphylactic shock)	K52.2x Allergic and dietetic gastroenteritis and colitis M31.0 Hypersensitivity angiitis T78.2x Anaphylactic shock, unspecified T78.4x Other and unspecified allergy M36.4x Arthropathy in hypersensitivity reactions classified elsewhere	558.3 Allergic gastroenteritis and colitis 446.20 Hypersensitivity angiitis, unspecified 446.21 Goodpasture's syndrome 446.29 Other specified hypersensitivity angiitis 995.0 Other anaphylactic reaction, Not elsewhere classified (NEC) 995.3 Allergy, unspecified, NEC 713.6 Arthropathy associated with hypersensitivity reaction
Hyperlipidemia	E78.49 Other hyperlipidemia E78.5 Hyperlipidemia, unspecified	272.4 Other and unspecified hyperlipidemia
Hypertriglyceride mia	E78.1 Pure hyperglyceridemia	272.1 Pure hyperglyceridemia

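### Table 3 counts a code for chemotherapy-caused agranulocytosis as a safety event, and nothing in the plan beyond esophageal cancer codes identifies children with cancer or under cancer treatment

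*Protocol*

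**What the plan says.** **Outcome codes (Protocol section 9.4.2, Table 3).** Agranulocytosis has two ICD-10-CM codes. One is D70.2, for other drug-induced disease. The other is "D70.1 Agranulocytosis secondary to cancer chemotherapy". The ICD-9-CM column has one code, "288.03 Drug induced neutropenia". A single inpatient or outpatient code during follow-up makes an event. The thrombocytopenia, leukopenia and pancytopenia rows contain no code that names chemotherapy. They rest largely on codes that state no cause, for example "D69.59 Other secondary thrombocytopenia D69.6 Thrombocytopenia, unspecified".

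**Baseline variables (section 9.4.3.2, Table 4).** The table starts under "History or presence of upper gastrointestinal anatomic or motor disorders" and continues with malabsorption, H. pylori and cystic fibrosis. Its malignancy codes are "C15 Malignant neoplasm of esophagus Z85.01 Personal history of malignant neoplasm of esophagus" on the ICD-10-CM side, and code 150 with "V10.03 Personal history of malignant neoplasm of esophagus" on the ICD-9-CM side. All sit in the row for esophageal or gastric motor disorders. The drug rows fall under "Diagnosed as having or has received treatment for esophageal, gastric, pyloric channel, or duodenal ulceration" and list only proton pump inhibitors and H2-blockers.

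**Other provisions.** The exclusions (9.3.2) concern preterm birth and low birth weight. Rates are broken down by GERD/EE subgroup and treatment duration (9.8). The two sensitivity analyses (9.8.1) concern the 30-day enrollment rule and the coding system. There is no comparator (9.1).

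**The concern.** A code whose label assigns the event to a different drug goes into the numerator of a rate reported as the safety experience of IV pantoprazole. In a single-arm study the reader has only the baseline description to judge how much of a rate reflects the underlying illness and its treatment. Here that description says nothing about cancer outside the esophagus, or about antineoplastic drugs. The report as planned could not show how many blood-count events arose in children under cancer treatment, or whether the proportion differs between the GERD subgroups and the group without GERD.

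**Working it through.** **1. The plan's own figures.** Table 5 in section 9.6 gives Wilson limits. With p = x/n and z = 1.96, the limits are [p + z²/(2n) ± z·√(p(1−p)/n + z²/(4n²))] / (1 + z²/n). For 15 of 7,489 this gives 0.0012 to 0.0033, and for 13 of 6,657 it gives 0.0011 to 0.0033. All 12 rows match when the rounded counts are used. The table's arithmetic is not in question; its lowest frequency, 0.002, serves as a reference in step 3.

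**2. Could any provision isolate chemotherapy-related events?**

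| Provision | What it does | What remains |
|---|---|---|
| Prior-history restriction (9.8) | Drops children already coded with the same outcome | A first coded event after index in a child on chemotherapy |
| Table 4 (9.4.3.2) | Flags esophageal cancer and acid suppressants | All other malignancy and all antineoplastic drugs |
| ICD-9-CM versus ICD-10-CM strata (9.8.1) | Splits by coding system | Causes within 288.03 and within cause-neutral codes |
| Strata by subgroup and duration (9.8) | Splits by GERD/EE and <4 versus ≥4 days | Cancer status |
| 25 most common codes (secondary objective 2) | Counts codes in GERD patients | Not linked to outcomes; no data for children without GERD |
| Limitations (9.10) | Says sensitive algorithms may overestimate some outcomes | Does not mention underlying disease or chemotherapy |

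None closes the gap.

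**3. Illustration of sensitivity, not an estimate.** The document gives no number of children on chemotherapy. Assume:

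- s = share on chemotherapy among the children in the outcome analysis: 1%, 3% or 5% (assumed)
- c = their risk of a first coded blood-count event in follow-up: 20% or 40% (assumed)
- r = risk in the other children: 0.2% (lowest Table 5 frequency)
- follow-up of 90 days for everyone, with no censoring: 90/365.25 = 0.2464 years

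Rate per 1,000 person-years = 1,000 × [s·c + (1−s)·r] / 0.2464. Without the chemotherapy patients it is 1,000 × 0.002 / 0.2464 = 8.1.

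For s = 1% and c = 20% in Cohort 1, chemotherapy events are 7,489 × 0.01 × 0.20 = 15.0 and other events are 7,489 × 0.99 × 0.002 = 14.8. Person-years are 7,489 × 0.2464 = 1,845. The rate is 29.8/1,845 = 16.2 per 1,000, and half the events come from 1% of the children.

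| s | Rate at c = 20% | Rate at c = 40% | Share of events from s |
|---|---|---|---|
| 1% | 16.2 | 24.3 | 50% to 67% |
| 3% | 32.2 | 56.6 | 76% to 86% |
| 5% | 48.3 | 88.9 | 84% to 91% |

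Cohort size cancels from the formula, so Cohort 2 gives the same rates.

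**The case against.** The strongest reply is that the study is descriptive. It has no hypotheses, aims at the incidence of coded outcomes rather than attribution to pantoprazole, and openly chooses broad code lists so that events are not missed. Section 9.10 admits that some rates may be too high. That explains breadth where the cause is unclear. It does not explain including a code whose label already names another cause.

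Some of the reply stands, and it limits what may be inferred:

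- A reader might infer that the protocol expects children with cancer in the cohorts. It does not say so. One code in a list proves no expectation, and the lists also carry esophageal cancer, Barrett's esophagus and NASH.
- A reader might infer that chemotherapy events can never be separated. D70.1 and D70.2 are distinct codes, so in the ICD-10-CM years the explicitly attributed events can be counted. The protocol does not plan this, and it does not help with 288.03 or the cause-neutral codes.
- Only the agranulocytosis row names chemotherapy. For the other three outcomes the effect is possible, not documented.
- The subgroups with and without GERD serve different objectives. The only comparison between strata that the protocol describes is ICD-9-CM versus ICD-10-CM.
- A flag identifies exposed children. It does not prove the cause of an individual 288.03 event.

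**Conclusion.** The point holds as a defect in the code lists. As written, the agranulocytosis rate includes events coded to another drug, and the plan has no variable that would reveal which children were under cancer treatment. The prior-history restriction reduces this but does not remove it.

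The size is unknown from the document. The illustration shows only that a small exposed share could dominate a rare blood-count outcome; its shares and risks are assumptions.

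A stronger claim is tempting: that chemotherapy events alone could be 2 to 12 times the rate the study could otherwise exclude. On 93 days of follow-up (3 treatment days plus 90), Cohort 1 has 7,489 × 93/365.25 = 1,907 person-years. A 1% share with 10% risk gives 7.5 events, or 3.9 per 1,000; a 2% share with 30% risk gives 44.9 events, or 23.6 per 1,000. The exact upper limit for zero events is 3.69/1,907, or 1.93 per 1,000, hence ratios of about 2 and 12. The arithmetic is right, but both inputs are assumed and the prior-history restriction is ignored, so the document does not support it as a finding.

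The change should be made before analysis. The defect affects how four outcomes are interpreted and does not undermine the study as a whole.

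**What to change.** 1. In Table 3, remove D70.1 from the agranulocytosis outcome, or report it on a separate line from D70.2.
2. Add to Table 4 a flag for malignancy or antineoplastic treatment, covering baseline and follow-up and tabulated by cohort and subgroup. Section 9.5 indicates that the dataset already holds coded diagnoses and administered medications.
3. Report agranulocytosis, leukopenia, thrombocytopenia and pancytopenia for all children, and again excluding those flagged at baseline. A new Table 4 row alone is not enough, because Table 4 variables are used only for description.
4. Do not exclude on the follow-up part of the flag, since that would select children on information arising after index. Instead, tabulate the events in children whose antineoplastic treatment began during follow-up.
5. Name this source of events in section 9.10.

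The cost is one more code list, repeated rates for four outcomes in each cohort, and slightly smaller denominators in the restricted rates.

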All statistical analysis will be performed in the two cohorts of interest, ie, infants aged 1 month to <1 year and in patients aged 1 to <2 years, separately using the Aetion Evidence Platform version 4.2. Descriptive statistics will be presented for the key variables to characterize the overall cohort treated with IV pantoprazole and the 3 subgroups defined based on the presence or absence of GERD and EE during the baseline period or on the index date. Incidence rates of outcomes of interest will be estimated as the number of patients with a specific outcome of interest during the follow-up period divided by the total person-time at risk and reported as incidence rate per 1,000 person-years with associated 95% confidence intervals (CIs). The CIs will be estimated using the exact method for event counts less than 10, assuming a Poisson distribution. Incidence rates for all outcomes of interest will be calculated in the overall cohort and in each of the 3 subgroups. Within the overall cohort and in the 3 subgroups, incidence rates will be estimated by duration of IV pantoprazole treatment (4 days, 4 days). Two sensitivity analyses will be performed as follows: (1) analysis will be repeated in both cohorts without exclusion criteria of at least 30-day enrollment prior to the index date to test the sensitivity to enforced 30-day enrollment period, and (2) analysis will be repeated in both cohorts, stratified by those patients identified via ICD-9-CM codes versus ICD-10-CM codes, respectively to test the sensitivity to ICD-9-CM versus ICD-10-CM coding for subgroup classification.

Milestones

Study protocol is planned to be submitted to the FDA by 20 August 2021 and study report is planned to be submitted to the FDA by 30 June 2022.

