GERD without EE*	K21.0	GERD with esophagitis	530.10, 530.11, 530.12, 530.19	Esophagitis unspecified Reflux esophagitis, Acute esophagitis, Other esophagitis
	K21.9	GERD without esophagitis	530.81	Esophageal reflux
GERD with EE	K21.0, K21.9	GERD with or without esophagitis	530.10, 530.11, 530.12, 530.19, 530.81	Esophagitis unspecified Reflux esophagitis, Acute esophagitis, Other esophagitis Esophageal reflux
	AND			
	K22.1	Ulcer of esophagus	530.2	Ulcer of esophagus

^{*} Patients with any of the listed ICD-9-CM or ICD-10-CM codes and no ICD-9-CM code of 530.2 or ICD-10-CM code of K22.1 during the baseline period or on the index date will be included in the GERD without EE subgroup.

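### The Table 4 comorbidity row for esophageal or gastric motor disorders contains the codes that define GERD and EE, so in the GERD subgroups it mostly restates subgroup membership

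*Protocol*

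**What the plan says.** Table 4 (Protocol Section 9.4.3.2) lists comorbidities and the codes that identify them. One row is labelled "Esophageal or gastric motor disorders (eg, scleroderma"). Its ICD-10-CM list contains the run "K20 Esophagitis K21 Gastro-esophageal reflux disease K22 Other diseases of esophagus", and its ICD-9-CM list contains "530 Diseases of esophagus 787.1 Heartburn". The remaining entries are:

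- esophageal cancer and a personal history of it (C15, Z85.01, 150, V10.03)
- gastroparesis (K31.84, 536.3)
- postgastric surgery syndromes (K91.1, 564.2)
- heartburn (R12), the ICD-10-CM counterpart of 787.1
- dyspepsia (K30, 536.8)
- esophageal disorders in diseases classified elsewhere (K23)
- congenital esophageal anomalies (Q39, 750.3, 750.4)

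Table 1 (Section 9.3.3) defines the subgroups. The GERD part of the EE definition, described as "GERD with or without esophagitis", uses K21.0 and K21.9, or the ICD-9-CM codes "530.10, 530.11, 530.12, 530.19, 530.81". The subgroup without EE uses the same seven codes. EE requires K22.1 or 530.2 in addition. The third subgroup has none of the Table 1 codes.

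The time windows differ. Subgroups rest on the "presence or absence of GERD and EE during the baseline period or on the index date" (Section 4, Data analysis; Section 9.3.3 agrees). Comorbidities are taken from the baseline period, with no mention of the index date (Section 9.4.3.2). Section 9.8 equates baseline with the time before the index date.

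Section 9.8 plans counts and percentages of the comorbidities for the overall cohort and for each of the three subgroups.

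**The concern.** A comorbidity reported by subgroup should tell the reader something that the subgroup label does not. This row shares its codes with the subgroup definition. In the two GERD subgroups, the focus of the primary objective, it would largely count the patients selected for having GERD and print the result under a motor-disorder label. In the third subgroup the same codes are excluded by definition, so the difference between the groups would be largely an artefact.

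The planned quality control would not catch this. Section 9.9 has the covariates built from the codes in the protocol, requires the protocol to be strictly followed, and has the analyses implemented twice. Two implementations of the same code list give the same wrong row.

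**Working it through.** The protocol states no figure for this row, so there is none to reproduce. The check has four steps.

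**1. Code containment.** Each Table 1 code is compared with the codes of the Table 4 row, first reading bare codes as categories, then as literal codes.

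| Table 1 code | Role | Category match | Literal match |
|---|---|---|---|
| K21.0, K21.9 | GERD | K21 | none |
| 530.10, 530.11, 530.12, 530.19, 530.81 | GERD | 530 | none |
| K22.1 | EE | K22 | none |
| 530.2 | EE | 530 | none |

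As categories, 7 of 7 GERD codes and 2 of 2 EE codes fall inside the row. As literal codes, 0 of 9 do.

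**2. Prevalence in a GERD subgroup, category reading.** Let q be the share of the subgroup whose only GERD code is on the index date. Let r be the share of those patients with some other code of the row in baseline. The remaining 1 − q have a baseline GERD code and are positive automatically. So

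prevalence = (1 − q) + q·r = 1 − q(1 − r).

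The protocol gives neither q nor r; the values below are assumptions.

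| q | r = 0 | r = 0.3 |
|---|---|---|
| 0% | 100% | 100% |
| 5% | 95% | 96.5% |
| 10% | 90% | 93% |
| 20% | 80% | 86% |
| 30% | 70% | 79% |

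For example, q = 20% and r = 0.3 give 1 − 0.20 × 0.70 = 0.86. The result is exactly 100% if q = 0, if r = 1, or if the index date is counted as baseline. The gap below 100% depends mainly on when GERD was coded, not on how common motor disorders are.

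**3. The no-GERD subgroup.** All nine Table 1 codes are excluded there. The row can still be positive through its other codes, such as gastroparesis, K20, Q39, the rest of K22, or members of 530 outside Table 1 (530.3, 530.6, 530.13, 530.85). It varies in this subgroup but is not specific to motor disorders.

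**4. Label against content.**

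- The titles of C15, Z85.01, 150 and V10.03 (cancer), K20 (esophagitis), R12 and 787.1 (heartburn) and Q39 (malformations) name no motor disorder. The same is true of 750.3 and 750.4.
- No listed code is described as scleroderma, the label's own example.
- Read as categories, the parents absorb codes that have rows of their own: strictures, webs and diverticula (K22.2, K22.5, Q39.3, Q39.4, 530.3, 530.6), Barrett's esophagus (K22.7x, 530.85) and eosinophilic esophagitis (K20.0, 530.13). Code 750.3 is listed outright in two rows.

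**The case against.** **The matching rule is not stated.** Table 4 marks some codes with a wildcard (K56.69x, K22.7x, K27.x, 277.0x) and leaves K21 and 530 bare. It also lists E84.8 beside bare E84, which would be redundant if E84 meant the whole category. This stands as an ambiguity. The category reading remains the natural one: "K21 Gastro-esophageal reflux disease" and "530 Diseases of esophagus" carry category titles, and bare category codes are used throughout the table (K25, K26, K28, K50, K57, K90, 531 to 534, 555, 579). Literal matching would undermine those rows too. It would also leave K21 and 530 with nothing to contribute from the GERD codes, which is no defence of listing them.

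**Stronger statements are tempting but not supported.** A reader might infer that the row is 100% in both GERD subgroups by construction. The two time windows do not allow that, because a patient coded for GERD only on the index date enters a GERD subgroup without triggering the row. A reader might also infer that the row measures nothing. Gastroparesis gives it some motor content, and it varies in the no-GERD subgroup. Nor is that subgroup barred from being positive through 530 as a whole, since Table 1 does not use every code under 530.

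**The consequences are limited.** The study has no comparator and no hypotheses. The row plays no part in eligibility, subgroup assignment, incidence rates or the definition of the sensitivity analyses. Table 4 prints its codes, so a careful reader could see the overlap. All of this is correct and bounds the seriousness. It does not make the definition right.

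**Conclusion.** The point holds as a defect in a stated definition. Under category matching, the row is positive for every patient with a baseline GERD code. It is therefore close to 100% in both GERD subgroups as long as few patients are coded only on the index date. How far below 100% it falls cannot be worked out from the protocol.

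Under either matching rule the row is a poor measure of what its label says. It is circular if codes are categories, and it still mixes in unrelated conditions if they are literal. The error would mislead in the descriptive comorbidity tables and nowhere else, but it should be corrected because the remedy is cheap and the planned quality control would reproduce it.

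**What to change.** Edit the row in Table 4:

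1. Remove the Table 1 codes and the entries that are not motor disorders: K21, K20, R12 and 787.1, C15, Z85.01, 150 and V10.03, and Q39 with its ICD-9-CM counterparts 750.3 and 750.4.
2. Replace the parents K22 and 530 with only those subcodes that name an esophageal motility disorder. Deleting the parents without replacement would leave a row named for the esophagus with no specific esophageal motility code.
3. Keep gastroparesis (K31.84, 536.3). Decide explicitly whether K23, K30 and 536.8, and K91.1 and 564.2 belong.
4. Add a scleroderma code or drop that example from the label.
5. Report malignancy or other esophageal disease in separate rows if wanted.

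State once, for the whole of Table 4, whether bare codes are matched as categories and whether the index date counts for comorbidities.

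The cost is a code-list revision and a rebuild and recheck of one covariate if it has already been programmed. Stating the matching rule or window may also change how other Table 4 rows are built. Cohort size, subgroup assignment and incidence rates do not change.

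### Table 4 operationalizes an ulceration comorbidity only through PPI and H2-blocker drug codes, so acid-suppressant use is reported as, or filed under, ulceration in the baseline tables

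*Protocol*

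**What the plan says.** Section 9.4.3.2 identifies each comorbidity by the "presence of at least one ICD-9-CM/ICD-10-CM diagnosis code or NDC/HCPCS codes identified using all available data during the baseline period" and refers to Table 4 for the codes.

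The disease rows in the first part of Table 4 carry ICD-10-CM and ICD-9-CM codes. Peptic ulcer disease, for example, is given as "K25 Gastric ulcer K26 Duodenal ulcer K27.x Peptic ulcer, site unspecified K28 Gastrojejunal ulcer", with 531-534 on the ICD-9-CM side. After the cystic fibrosis row comes the label "Diagnosed as having or has received treatment for esophageal, gastric, pyloric channel, or duodenal ulceration", with nothing in either ICD column. Directly below it is the line "Proton pump inhibitors", where the column heads change to "Operationalization: NDC code" and "Operationalization: HCPCS code". Five PPIs follow, then an H2-blocker subheading and four drugs. The HCPCS entry for famotidine is "J3490 Unclassified drugs".

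Esophageal ulcer is coded explicitly only in Table 1 (Section 9.3.3), as K22.1/530.2. For a child who has a listed GERD code, the condition in its footnote reads "no ICD-9-CM code of 530.2 or ICD-10-CM code of K22.1 during the baseline period or on the index date will be included in the GERD"; the subgroup meant there is the one that lacks EE.

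Section 9.8 uses comorbidities to describe the overall cohort and the three subgroups, separately for the two age cohorts.

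**The concern.** The label has two halves and the codes support neither. A diagnosis of ulceration needs a diagnosis code, and there is none. Treatment for ulceration needs a drug linked to that indication, and the rule asks only for the drug. PPIs and H2-blockers are also given for reflux, and reflux defines the study's primary population. A row built this way would largely record prior acid suppression.

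The baseline tables tell a reader what kind of children lie behind each set of incidence rates. If one line makes the GERD subgroups look as though they carry much ulcer disease when they mainly carry acid-suppressant prescriptions, the reader may wrongly explain differences in rates between subgroups by ulcer disease.

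The quality control in Section 9.9 would not catch this. Measures are built from the codes in the protocol, which is to be followed strictly, so the independent second implementation would reproduce the same definition.

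**Working it through.** The protocol states no figure for this variable, so there is nothing to recompute. The check is a comparison of codes and rules.

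**1. What sits under the ulceration label.** ICD codes: 0. Drugs: 5 PPIs (omeprazole, esomeprazole, lansoprazole, rabeprazole, pantoprazole) + 4 H2-blockers (famotidine, cimetidine, ranitidine, nizatidine) = 9. These are the only NDC/HCPCS codes in Table 4. The clause in Section 9.4.3.2 that lets a drug code identify a comorbidity can therefore refer only to this block.

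**2. What the rule does if the nine drugs form one flag.** Illustrative children, classified by the printed codes:

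| Child, baseline record | Subgroup (Table 1) | Peptic ulcer row | Ulceration label |
|---|---|---|---|
| K21.9, listed lansoprazole NDC, no ulcer code | GERD without EE | No | Yes |
| K21.0 and K22.1, no listed drug | GERD with EE | No | No |
| K26, no GERD code, no listed drug | No GERD or EE | Yes | No |
| K21.9, J3490 billed for an unrelated drug | GERD without EE | No | Yes |

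The first and fourth children are positive with no evidence of an ulcer. The second and third have a coded ulcer and are negative on this line.

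**3. What happens if each drug is its own line.** No child is flagged as ulcerated, but nine medication rows appear under an ulceration heading. The label is then wrong although the counts may be right. The exception is famotidine, where J3490 would still count other drugs.

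**4. Factors acting in different directions.** J3490 can only add false positives. The short package-code lists work the other way: one NDC each for omeprazole and rabeprazole, three for esomeprazole, four for lansoprazole. Many children on acid suppressants may not be flagged. The pantoprazole entries (S0164 and the NDCs ending 0923-51, -55 and -60) are also exposure codes in Table 2. The index date is the first IV administration in the study period, and Section 9.8 places baseline before it, so these codes should rarely fire. They would matter if an analyst counted the index date as baseline.

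**5. Where the variable is used.** Eligibility (Sections 9.3.1 and 9.3.2), subgroups (Table 1), outcome-specific exclusions, follow-up and rates (Section 9.8) use other code lists. The ulceration entry feeds only the descriptive tables.

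**The case against.** The strongest reply is that the line is a section heading and not a variable. It has empty cells, is followed by drug-class subheadings and one line per drug, and Table 4 opens in a similar way, with a general heading above the coded rows. No sentence says the nine drugs are pooled. The empty cells might be an artefact of table layout, and the statistical analysis plan could settle how the drugs are tabulated. This stands as a reason not to assert that GERD children will be counted as having ulcers. It does not rescue the label: on the heading reading, prior acid suppression is still filed under ulceration. Nor was the definition left open, since the protocol fixes it at code level.

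Three stronger inferences a reader might draw are not supported:

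- *That the line contradicts the EE/no-EE split.* The split uses Table 1 codes only. The label also covers gastric, pyloric and duodenal sites, so a child without EE could properly be positive.
- *That diagnosed ulcers vanish from the baseline description.* Gastric, duodenal, peptic and gastrojejunal ulcers have their own row, and esophageal ulcer among GERD patients defines a subgroup. They are missed only on this line.
- *That a given share of GERD children would be misreported.* The protocol gives no prevalence of acid-suppressant use or of ulcer, so any percentage would be one assumption divided by another.

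**Conclusion.** The point holds as a defect of definition and labelling. On the printed rule, acid-suppressant use with no ulcer indication either counts as ulceration or appears under an ulceration heading; which of the two depends on whether the drugs are pooled, and the protocol does not say. J3490 is unsuitable as evidence of famotidine on either reading.

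The importance is minor. The study has no comparator and no hypotheses, and the variable appears only in the baseline tables for each cohort and its three subgroups. A reader might infer that the safety estimates are biased. They are not, because rates, subgroup assignment and outcome exclusions do not draw on this entry. The size of the misclassification cannot be stated from the protocol. The conclusion assumes that the ICD cells beside the label are truly blank, which the NDC/HCPCS column heads directly below make the natural reading.

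**What to change.** In Table 4:

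1. Relabel the drug block as prior PPI/H2-blocker use in the baseline period and report it as medication rows.
2. Remove J3490 as evidence of famotidine use.
3. If an ulceration row is wanted, define it by diagnosis codes already in the protocol: K22.1/530.2 together with K25-K28/531-534.

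The cost is a few lines in Table 4 and one re-run of the baseline tables. No new data are needed and the incidence analyses are unchanged. There are two downsides. A child treated for an ulcer that was never coded would appear only in the medication rows. The ulceration row would also partly overlap the existing peptic ulcer row, which a table footnote can state.
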